3.3 Definition of Baseline values

Unless otherwise noted, baseline is defined as the last assessment before first dosing in the previous RLS study of rotigotine (SP1006).

3.4 Protocol deviations

Important protocol deviations are deviations from the protocol which potentially could have a meaningful impact on study conduct or on the primary efficacy, key safety, or PK outcomes for an individual subject. The criteria for identifying important protocol deviations will be defined within the appropriate protocol-specific document. Important protocol deviations will be reviewed as part of the ongoing data cleaning process and data evaluation. All important deviations will be identified and documented prior to database lock.

3.5 Analysis sets

3.5.1 Enrolled Set (ES)

The ES will consist of all subjects with a signed informed consent form.

3.5.2 Safety Set

The Safety Set (SS) will consist of all subjects who have at least one patch (rotigotine) applied. This analysis set will be used for all analyses except for the pharmacokinetic data.

3.5.3 Pharmacokinetic Set

The Pharmacokinetic Set (PKS) will consist of all subjects from the SS who provided at least 1 valid post-dose plasma concentration of unconjugated rotigotine.

Due to early stopping of the study, the analyses planned using the PKS will no longer be performed.

3.6 Treatment assignment and treatment groups

Generally, all summaries/analyses will be performed using the final dose group, i.e., the starting dose of the maintenance period. In addition, some summaries/analyses will be present for longest dose or actual dose.

3.7 Center pooling strategy

Not applicable.

3.8 Coding dictionaries

Adverse events and medical history will be coded using the most recent version of Medical Dictionary for Regulatory Activities (MedDRA 25.1). Prior or concomitant medication will be coded using the most recent version of the World Health Organization Drug Dictionary (WHO DD MAR/2022).

3.9 Changes to protocol-defined analyses

Statistical analysis and generation of tables, figures, subject data listings, and statistical outputs will be performed using SAS Version 9.3 or higher. None of the planned analyses require SAS Version 9.4 and can all be performed on SAS Version 9.3.

Analyses will not be performed as defined in the study protocol due to early study termination. All data will be listed, and key summary tables will be produced.

4 STATISTICAL/ANALYTICAL ISSUES

4.1 Adjustments for covariates

Not applicable.

4.2 Handling of dropouts or missing data

Subjects who prematurely discontinue the study will be evaluated based on the data collected at each visit attended. If the premature discontinuation occurs at a scheduled visit, data collected at that visit will be summarized at the scheduled visit time point. Otherwise, the data will be attributed to the next scheduled visit for the purpose of by-visit endpoint summaries.

With respect to AEs, events with missing intensity will be assumed to be severe. Events with missing relationship to study medication per the investigator will be assumed to be related. Events with a missing answer to the question “Serious Adverse Event?” will be considered serious.

4.2.1 Missing efficacy data

For subjects who prematurely withdraw for any reason before EoM, values for planned efficacy assessments scheduled at subsequent visits will not be imputed. Efficacy assessments must be performed no later than 1 day after the last patch removal to be utilized for analysis (valid measurements).

For IRLS analysis if any item is missing, the IRLS sum score will be not calculated. Missing IRLS baseline value will be regarded as an important protocol deviation.

4.2.2 Missing and Incomplete Dates for Adverse Events and Concomitant Medication

For analyses of AEs and concomitant medication usage, a complete date must be established in order to correctly identify the AE or medication as occurring during treatment in the study or not. For the purposes of imputing missing date or missing components of partially-reported start and stop dates for AEs and for medication use, the algorithms listed below will be followed. Start and

stop dates of AEs or concomitant medication will be displayed as reported in the subject data listings (i.e., no imputed values will be displayed in data listings).

- Missing start day, but month and year present:

If the first patch application occurred in the same month and year as the occurrence of the AE/medication, the start day of the event/medication will be assigned to the day of first patch application.

Otherwise, the start day will be set to the 1st day of the month.

- Missing start day and month, but year present:

If the first patch application occurred in the same year as the occurrence of the AE/medication, the start day and month will be assigned to the date of first patch application.

Otherwise, the start day and month will be set to January 1st.

- Missing end day, but month and year present:

The end day will be set to the last day of the month.

- Missing end day and month, but year present:

The end day and month will be set to the date of study termination or the date equivalent to 30 days after last patch removal, whatever occurs later.

However, if the study termination year and year for the date which is 30 days after the last patch removal are greater than the event/concomitant medication year, the day and month are to be set to December 31st.

- Completely missing start date:

An AE will be considered as occurring during treatment.

Medications with an unknown stop date or a stop date after the date of the first patch application will be considered as concomitant medication but not as prior medication.

- Completely missing stop date:

Adverse events with a completely missing stop date will be considered ongoing.

Medications with a start date before the first patch application will be considered as prior and concomitant medications. Medications with a start date during the Treatment Period will be considered as concomitant medication.

- Imputed stop date prior to imputed start date:

If the year of start date is the same as the year of first patch application and the stop date is after the date of first patch application, then set the start date to the date of first patch application.

Otherwise, set the start day and month to January 1st of the start year.

In the event of ambiguity or incomplete data which makes it impossible to determine whether a medication was concomitant, or an adverse event was treatment emergent, the medication will be considered as concomitant or the adverse event will be considered treatment emergent.

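### SAP 4.2.2: a year-only end date is imputed about 335 to 364 days too early when only one of the two reference dates crosses into the next year, which can reclassify partial-date records of subjects who stopped early

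*SAP*

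**What the plan says.** SAP Section 4.2.2 gives this rule for an end date with a known year but no day or month: "The end day and month will be set to the date of study termination or the date equivalent to 30 days after last patch removal," taking whichever is later. An exception follows. It applies "if the study termination year and year for the date which is 30 days after the last patch removal are greater than the event/concomitant medication" end year, and in that case "the day and month are to be set to December 31st". So 31 December is used only when both reference dates lie in a later year than the recorded one.

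Four other rules decide what happens next:

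- **Partial start date (4.2.2).** If only the day is missing, the start is the first of the month, or the first-patch date when that falls in the same month. If day and month are missing and first patch is in the same year, "the start day and month will be assigned to the date of first patch application".
- **Imputed stop before imputed start (4.2.2).** The start moves to first patch if it shares the first-patch year and the stop is after first patch. "Otherwise, set the start day and month to January 1st of the start year".
- **Catch-all (end of 4.2.2).** Where ambiguous or incomplete data leave the status undeterminable, the AE counts as treatment emergent and the medication as concomitant.
- **Definitions.** Section 10.2 decides TEAE status by the start date, from first patch to 30 days after last patch removal. Section 6.4 requires a concomitant medication to have been used in the Treatment Period.

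**The concern.** The exception is there to stop a date from the following year being forced into the recorded year. It misses the case where only one of the two dates crosses 31 December. The rule is evidently meant to return a late, conservative end date, but here it returns one of the earliest dates of the year.

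The stop-before-start rule can then overwrite a recorded start month and place the whole event before first patch. Occurrence of TEAEs is a primary safety variable (SAP 2.1.2.1). Because listings show dates as reported, a listing could show an AE starting in November on treatment while the TEAE table leaves it out.

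**Working it through.** The plan gives no figure to reproduce, so the check starts with two control cases in which the rule works.

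Notation: Y is the recorded end year, T the study termination date, and P the last patch removal date plus 30 days. The literal rule is: if year(T) > Y and year(P) > Y, the end date is 31 Dec Y; otherwise it is the day and month of the later of T and P, in year Y.

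| Case (Y = 2022) | Last patch removal | T | P | Literal end date | With the fix |
|---|---|---|---|---|---|
| Both in Y | 20 Oct 2022 | 20 Nov 2022 | 19 Nov 2022 | 20 Nov 2022 | 20 Nov 2022 |
| Both in Y+1 | 20 Dec 2022 | 15 Jan 2023 | 19 Jan 2023 | 31 Dec 2022 | 31 Dec 2022 |
| Only P crosses | 10 Dec 2022 | 10 Dec 2022 | 9 Jan 2023 | 9 Jan 2022 | 31 Dec 2022 |
| Only T crosses | 29 Nov 2022 | 3 Jan 2023 | 29 Dec 2022 | 3 Jan 2022 | 31 Dec 2022 |

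**Size of the date error (non-leap year).**
- Third row: 365 − 9 = 356 days. Fourth row: 365 − 3 = 362 days.
- If only P crosses, last patch removal lies between 2 and 31 December and P between 1 and 30 January. The error is 365 − 30 = 335 to 365 − 1 = 364 days.
- If only T crosses, and by no more than 5 days after P (the follow-up window in Protocol Table 5-1), the imputed date is 1 to 5 January. The error is 360 to 364 days.

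**Effect on an AE.** Take the third row with first patch on 1 Mar 2022, and an AE with start Nov 2022 and end 2022.
1. The start is imputed as 1 Nov 2022 and the end as 9 Jan 2022.
2. The stop precedes the start and is not after first patch, so the start is reset to 1 Jan 2022.
3. 1 Jan 2022 is before 1 Mar 2022, so under Section 10.2 the AE is not a TEAE.
4. With the end at 31 Dec 2022, no reset occurs, the start stays at 1 Nov 2022 and the AE is a TEAE.

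**Effect on a medication.** For the same subject, take a medication begun in 2020 with end 2022. The imputed end of 9 Jan 2022 precedes first patch, so the imputation steps make it prior only. The catch-all would make it concomitant.

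**When classification can change.** First patch must fall in year Y after the imputed January date.
- If only P crosses, last patch removal minus the imputed end date is 365 − 30 = 335 days. In the example, 10 December is day 344 and 9 January is day 9, and 344 − 9 = 335.
- If only T crosses, with T 31 to 35 days after last patch removal, the limit is 365 − 31 = 334 down to 365 − 35 = 330 days.
- The worked subject has 344 − 60 = 284 days from first patch to last removal, so is exposed.
- The earliest in-window Visit 9 in Protocol Table 5-1 is Day 360 − 14 = 346, which is 345 days after Day 1. Completers therefore keep their classification.
- With first patch on 25 Nov 2021, the reset start of 1 Jan 2022 is still after first patch and nothing is lost.

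**How often the two dates straddle.** Assume termination dates are spread evenly over 365 days.
- Termination on the day of last patch removal, with no follow-up visit: 30/365 = 8.2%.
- Termination at a follow-up visit up to 5 days either side of day 30: at most 5/365 = 1.4%.

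**The case against.** **The catch-all rescues these records.** For the medication this is a fair reading: the recorded data cannot show whether use continued past first patch, which is the situation that sentence describes. But the SAP does not say whether the catch-all overrides a date the algorithm has already completed. What can be claimed is that two rules give opposite answers with no stated order. The catch-all helps the AE less, because the recorded November start already places it on treatment and the algorithm returns a definite wrong answer.

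**A programmer would carry over the whole later date.** An end of 9 Jan 2023 would avoid the reset and keep both classifications. It would also contradict the recorded year and the wording "The end day and month will be set to the date of study termination", which fills day and month only. The literal reading is the better supported, but the text leaves room for both.

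**The reach is very small.** This stands. Protocol Table 5-1 requires every subject to complete the follow-up visit, so 8.2% describes only those who do not. AEs with a complete start date are unaffected. An AE with no start date at all is treated as on treatment by Section 4.2.2 and is not counted here. The analyses are descriptive after early termination, all AEs are listed, and nothing in the documents shows that such a record exists.

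**Conclusion.** The rule is wrong as written when the two reference dates straddle 31 December and the recorded year is the earlier one. On the literal text the end date is then about 335 to 364 days too early.

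A reader might infer that the rule removes on-treatment events from the TEAE tables generally, or that 8.2% of subjects lose records. The documents support neither. Reclassification needs a year-only end date, a straddle, and first patch in the same calendar year after the imputed date (under about 335 days of treatment). For AEs it also needs a partial start date. Early termination of the study makes short treatment plausible, but the documents give no durations. A reader might also infer that the medication certainly drops out; the catch-all prevents that conclusion.

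The 1.4% and 8.2% count straddles, not lost records, and rest on evenly spread termination dates. The number of affected records is unknown and probably small. This is a minor wording defect, but each record reclassified under the literal steps moves in the non-conservative direction.

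**What to change.** In SAP Section 4.2.2, replace the exception with: *If the later of the study termination date and the date 30 days after last patch removal falls in a year after the event/medication year, set day and month to December 31st.*

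Both control cases are unchanged and both straddle cases return 31 Dec 2022. The worked AE stays a TEAE, and for the worked medication the algorithm and the catch-all then agree. The stop-before-start rule needs no change for this point. A clause forbidding any change to a recorded start month would be unnecessary once the end date is right, and it would leave genuine stop-before-start records without a result.

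The cost is one sentence in the SAP and one condition in the date-imputation program. No additional data are needed.

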11.1 Adverse events

11.1.1 Definitions

11.1.1.1 Adverse event

An AE is any untoward medical occurrence in a patient or clinical investigation subject administered a pharmaceutical product that does not necessarily have a causal relationship with this treatment. An AE can therefore be any unfavorable and unintended sign (including an abnormal laboratory finding), symptom, or disease temporally associated with the use of a medicinal (investigational) product, whether or not related to the medicinal (investigational) product.

In order to ensure complete safety data collection, all AEs occurring during the study (ie, after the signing of the Informed Consent form), including any pretreatment and posttreatment periods required by the protocol, must be reported in the eCRF even if no IMP was taken but specific study procedures were conducted. This includes all AEs not present prior to the initial visit and all AEs that recurred or worsened after the initial visit. Adverse events present at Visit 9 for SP1006 will have to be recorded for RL0007 since this is Visit 1 and the start of this study.

Signs or symptoms of the condition/disease for which the IMP is being studied should be recorded as AEs only if their nature changes considerably or their frequency or intensity increases in a clinically significant manner as compared to the clinical profile known to the investigator from the subject's history or the Baseline Period.

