2.1.2 Safety variables

2.1.2.1 Primary safety variables

The primary safety variables are:

- Occurrence of treatment-emergent adverse events (TEAEs)
- TEAEs leading to permanent withdrawal of study medication

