10.2 Adverse events

Adverse events will be documented throughout the entire study on an ongoing basis. TEAEs are defined as events that started during the Treatment Period or within 30 days following the end of the Treatment Period (i.e., on or after the date of first patch application and within 30 days following the date of last patch removal) or any unresolved event already present before administration of treatment that worsens in intensity following exposure to the treatment. For AEs with a partial or missing start date, the imputation rules as described in [Section 4.2.2](#) will be applied.

Adverse events with a missing start date are defined as treatment-emergent if the end date of the AE is not on or before the date of first patch application.

An AE with action taken regarding study medication reported on the AE page of the eCRF as “drug permanently withdrawn” will be regarded as an AE leading to discontinuation of study medication.

Adverse events which have the question “Serious Adverse Event?” answered “yes” are considered serious.

Treatment emergent AEs will be tabulated by MedDRA SOC, High Level Term (HLT) and PT. The number and percentage of subjects experiencing each event at least once will be summarized in addition to the number of events. In summaries of TEAEs by relationship and intensity, respectively, the number of events will not be presented.

All summaries will be sorted alphabetically by SOC and HLT and by frequency of events (PT) within HLTs. If there is more than one PT with the same frequency these events will be sorted alphabetically.

An overview of the incidence and frequency of all TEAEs, serious TEAEs, TEAEs leading to discontinuation of study medication, related TEAEs, severe TEAEs, all deaths, and TEAEs leading to death will also be provided.

The following tabular summaries will be presented also.

- TEAEs
- TEAEs by intensity
- TEAEs by maximum intensity
- TEAEs by relationship to study medication per the Investigator
- Serious TEAEs
- Serious TEAEs by Relationship to study medication per the Investigator
- non-serious TEAEs above reporting frequency threshold of 5%

Individual subject data listings will be presented for all AEs.

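### SAP 4.2.2 and 10.2 disagree on AEs with no start date that ended before, or on, the day of the first patch, and no text says which rule prevails

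*SAP*

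**What the plan says.** - **SAP 4.2.2** explains why dates are completed: "a complete date must be established in order to correctly identify the AE or medication as occurring during treatment in the study or not". Under the item for a completely missing start date, the AE rule is "An AE will be considered as occurring during treatment". It has no condition on the end date. The medication rule in the same item does have one: "Medications with an unknown stop date or a stop date after the date of the first patch application will be considered as concomitant medication".
- **SAP 4.2.2, closing paragraph**, is a fallback. Where the data make it impossible to tell whether an AE was treatment-emergent, the AE is counted as treatment-emergent.
- **SAP 10.2** sets the TEAE window. The event starts on the day of first patch or later, up to 30 days after last patch removal, or is an unresolved earlier event that worsens after exposure. It then says that the 4.2.2 rules apply to partial or missing start dates. Its next statement is that AEs for which none is recorded "are defined as treatment-emergent if the end date of the AE is not on or before the date of first patch application".
- **SAP 3.2.2** begins the Treatment Period on the day of first patch and ends Screening the day before.
- **Protocol 11.1.1.1** collects AEs from consent, including before treatment, and adds: "Adverse events present at Visit 9 for SP1006 will have to be recorded for RL0007".
- **SAP 2.1.2.1** lists occurrence of TEAEs first among the primary safety variables.

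**The concern.** Two sections give different answers for the same event, and the variable they feed is primary. Section 10.2 refers to 4.2.2 and then states its own condition, without saying that the condition overrides. A programmer who takes 4.2.2 literally would assign to RL0007 treatment an event that was over before the first RL0007 patch. A programmer who takes 10.2 literally would drop an event that may have begun on the first day of treatment. The medication rule beside it has an end-date test, so the bare AE rule looks like an omission.

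Pre-dose events are on the database by design. Visit 1 is planned four days before first patch, and a subject who cannot continue directly may enrol as late as the SP1006 safety follow-up visit (notes to Protocol Table 5-1). An event carried over from SP1006 can therefore resolve before the first RL0007 patch.

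**Working it through.** The plan gives no figure to reproduce here, and no sample size calculation was made (SAP 2.3). The check applies both rules to each possible end date.

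**Step 1: define the cases.** Let D be the AE's end day relative to first patch, with D = 0 on the day of first patch. The start date is completely missing.
- 4.2.2 counts the event for every D.
- 10.2 counts it if D > 0 or D is missing. Its sentence says *if* rather than *only if*, but as a definition it excludes the rest.
- The 10.2 window can be met only if the event could have started, or worsened, on day 0 or later. An event cannot start or worsen after it has ended, so this needs D ≥ 0 or D missing.

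**Step 2: compare.**

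| End date | 4.2.2 | 10.2 rule | Could meet 10.2 window? | Rules agree? |
|---|---|---|---|---|
| Before first patch (D < 0) | counted | not counted | no | no |
| Day of first patch (D = 0) | counted | not counted | yes | no |
| After first patch (D > 0) | counted | counted | yes | yes |
| Missing | counted | counted | yes | yes |

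The rules differ in two of the four cases, and a different section is at fault in each. For D < 0 the error lies in 4.2.2. For D = 0 it lies in 10.2, because the event could have started that day, which 3.2.2 places in the Treatment Period. This assumes that nothing else on record dates the onset earlier.

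**Step 3: does the fallback settle it?** For D < 0 it does not: a known end date before first patch determines the status, so nothing is ambiguous. For D = 0 the status cannot be determined, so the fallback counts the event and contradicts the 10.2 exclusion.

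**Step 4: which events are involved?** Only those with no start date at all. A start date with a year, or a month and year, has its own rules in 4.2.2.

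**Step 5: size.** SAP 10.2 counts each subject once per event category. One reclassified event changes overall TEAE incidence only if that subject has no other TEAE. The change is then 100/n percentage points, where n is the number treated. The documents do not give n after early termination, so the values below are assumptions, apart from the planned maximum of 138.

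| n | 100/n |
|---|---|
| 10 | 10.0 |
| 20 | 5.0 |
| 50 | 2.0 |
| 138 | 0.7 |

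Safety tables are also shown by final dose group (SAP 10), where the denominators are smaller and the ceiling is correspondingly higher.

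**Step 6: test the proposed rule.** If both sections count the event unless D < 0, they agree in all four cases, and no event that could meet the window is dropped.

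**The case against.** The best defence is that Section 10.2 is the only place that defines a TEAE. Section 4.2.2 handles dates and speaks of events during treatment. In 10.2 the cross-reference comes first and the end-date condition follows directly, which reads naturally as a general rule and then a specific one. A programmer deriving the TEAE flag would probably work from 10.2. This carries weight: a reader might infer two rival definitions of the primary variable, or that two programmers are bound to get different counts, and the documents support neither. What stands is that precedence is nowhere stated, and that 4.2.2 gives its purpose as deciding what happened on treatment.

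Over-counting might also be called deliberate caution, since SAP 4.2 takes missing intensity as severe and missing relationship as related. Those rules fill in an unknown. A known end date before first patch is not unknown.

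The case is also rare. Recording pre-dose AEs does not explain why one would have a known end date but not even a start year, and data-cleaning checks are planned (Protocol 12.3.2). That is right, and it limits the importance of the point. Any such event would also be visible, because all AEs are listed individually (SAP 10.2) with dates as reported (SAP 4.2.2).

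**Conclusion.** The inconsistency is real and in current text. Read literally, 4.2.2 counts an AE that ended before the first RL0007 patch, which cannot be treatment-emergent. The 10.2 condition excludes an AE that ended on the day of first patch, although that AE could meet 10.2's own window. Neither section is right as it stands.

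Two stronger readings go too far. A reader might infer that everything 4.2.2 adds beyond 10.2 is impossible as a TEAE; that holds only for events ending strictly before first patch. A reader might also infer that every affected subject shifts TEAE incidence by 100/n; that is a ceiling, reached only when the subject has no other TEAE.

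The point is minor. Few events are expected, the analysis is descriptive and cut back after early termination (SAP 3.9), and the ceiling per such subject runs from 0.7 points at n=138 to 10 points at n=10, with the treated n assumed. It is worth correcting because it affects a primary variable and costs little.

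**What to change.** In SAP 4.2.2, replace the AE rule for a completely missing start date with:

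> An AE with a completely missing start date is considered treatment-emergent unless its end date is before the date of first patch application.

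Put the same sentence in SAP 10.2 in place of its present end-date condition.

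Declare in the amendment that this moves the 10.2 cut-off from *on or before* to *before*. AEs with no start date that end on first-patch day then become TEAEs under 10.2, in line with its window and with the 4.2.2 fallback. AEs with no end date stay treatment-emergent, as under both present rules. The rule only classifies events, so no start date has to be imputed.

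The cost is two short edits and possibly a slightly higher TEAE count from same-day events. SAP Section 1 requires amendments to be final before database lock. If lock has passed, state the rule used in the study report.
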